5.4.2.3.2 Variables for supplementary analyses

5.4.2.3.2.1 Time to 12-week CDA up to EOS or per protocol exclusion

Time to 12-week CDA for the per protocol analysis is derived in the same way as for the variable for the main analysis, but only based on EDSS assessments (for onset and confirmation) conducted prior to first occurrence of a deviation leading to exclusion from per protocol [see Section 7.1.3]. Also, deaths due to MS are only considered up to that date. Subjects not experiencing a 12-week CDA event based on their per protocol data are censored at the last EDSS prior to per protocol exclusion without possible onset as for the main analysis.

5.4.2.3.2.2 Time to 12-week CDA up to EOT + 7

The variable for the main analysis described above will be repeated for 12-week CDAs up to EOT + 7 days. The onset date of the 12-week CDA must be up to EOT + 7 days; the confirmation of the 12-week CDA can be on-treatment or based on post-treatment

data. Otherwise the same rules as described in Section 5.4.2.3.1 apply. Subjects that are considered not to have 12-week on-treatment CDA are censored on the last EDSS assessment up to EOT + 7 days, following the same rules as described in the previous section.

5.4.2.3.2.3 Time to potential 12-week CDA up to EOS

12-week CDA requires confirmation of an EDSS increase by a scheduled EDSS assessment 12 weeks after progression onset. A potential onset at the end of the study may not be confirmed due to end of follow-up within the study. For time to potential 12-week CDA up to EOS all subjects censored in the main analysis with an EDSS increase at the last EDSS assessment in the study are considered as having a potential 12-week CDA, although the confirmation is missing. The onset date of the event for these subjects is the first EDSS increase after the last EDSS assessment without increase. Otherwise the same approach for derivation as described in Section 5.4.2.3.1 is followed.

5.4.2.3.2.4 Time to potential 12-week CDA up to EOS or per protocol exclusion

The time to potential 12-week CDA analysis is repeated for time to 12-week CDA up to EOS or per protocol exclusion.

5.4.2.3.2.5 Time to 12-week CDA up to EOS – alternative censoring

12-week CDA events and corresponding time to event are derived as above for the main analysis [see Section 5.4.2.3.1].

Subjects without 12-week CDA event are censored at their last scheduled EDSS assessment – 12 weeks (84 days).

This alternative censoring algorithm is applied (a) to ensure independence of censoring from the EDSS outcome and consequently avoid informative censoring and (b) to reflect that onset of 12-week CDA events can only occur 12 weeks prior to the last scheduled assessment.

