1. For all post-baseline EDSS assessments (scheduled or unscheduled) assess if the absolute change from baseline meets the EDSS increase criteria for disability accumulation, described above. Start with the first EDSS assessment that meets the criteria for EDSS increase. Onset date of the corresponding potential 12-week CDA is the EDSS assessment date.

2. Confirmation of EDSS increase:

a. An EDSS increase of a potential 12-week CDA has to be confirmed by an EDSS increase at a scheduled visit, at least 70 days*, from the onset date of the potential 12-week CDA.

* Note: As visits are scheduled every 12 weeks with a time window of ± 7 days for conducting the EDSS assessment, the minimum per-protocol allowed time difference between two EDSS assessments scheduled 12 weeks apart is 70 days (12 weeks = 84 days minus a 7-day visit time window for each of the 2 visits, i.e., 84 days – 14 days = 70 days).

EDSS assessments conducted during a relapse, i.e., from relapse start date (inclusive) to minimum of relapse end date and relapse start date + 90 days (exclusive) are not considered for confirmation.

If an EDSS increase cannot be confirmed due to no available EDSS assessment, but the subjects dies due to MS (experiences a relapse with outcome death, or death with reason ‘Multiple sclerosis’) the CDA is also considered confirmed, with confirmation date being the death date and onset date the initial EDSS increase.

b. A confirmed EDSS increase as per (a) is considered persistent if every EDSS score available (scheduled or unscheduled) between the onset and the confirmation date of a potential 12-week CDA meets the EDSS increase criteria. The initial EDSS increase is considered a 12-week CDA.

If any EDSS from onset to confirmation does not meet the EDSS increase criteria, the increase is not persistent and the initial EDSS increase is not considered a 12-week CDA.

3. Repeat step 2 for all EDSS assessments with an EDSS increase as per the criteria above for disability accumulation, starting with the first possible onset, by date, up to the last possible onset. Once a 12-week CDA is identified the algorithm can stop.

4. If at none of the assessments a 12-week CDA is identified, but the subject dies due to MS (experiences a relapse with outcome death) the subject is considered to have a 12-week CDA with onset date being the death date.

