5. If no 12-week CDA is identified, the subject is considered censored with the censoring date derived according to the rules below.

Censoring

Censoring date is defined as: Date of last EDSS assessment without an EDSS increase. Time to censoring is defined as censoring date minus date of randomization + 1.

Subjects without post-baseline assessment are censored on randomization date. Similar, subjects without CDA who have only EDSS assessments with an EDSS increase that cannot be confirmed, are censored on randomization date. For subjects without baseline EDSS score, missing values are assigned.

Handling of missing dates

Missing dates for EDSS assessments will be imputed as follows:

- Partial date: Maximum of 'lower limit', 'previous scheduled EDSS assessment according to the visit label' + 1 day (if available), and 'randomization date'
- Missing date: do not impute and exclude from analysis

Missing dates for relapse start and end dates will be handled as follows:

- Partial or missing relapse end date with available relapse start date: use relapse start date + 90 days or upper limit of partial end date if earlier.
- Partial relapse start date: If only day is missing, consider the relapse has started on the last day of the month (or on relapse end date – 1 day if earlier) and ended 60 days later or at (upper limit of a partial) relapse end date, if earlier. If the month or year are missing the relapse does not lead to non-consideration of an EDSS assessment.
- Missing relapse start date: Corresponding relapse does not lead to non-consideration of an EDSS assessment. Do not consider imputed relapse start dates.

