5.4.2.4.2 Variables for supplementary analyses

5.4.2.4.2.1 Time to 24-week CDA up to EOS or per protocol exclusion

Time to 24-week CDA for the per protocol analysis is derived in the same way as for the variable for the main analysis, but only based on EDSS assessments conducted prior to first occurrence of a deviation leading to exclusion from per protocol [see Section 7.1.3].

Also, deaths due to MS are only considered up to that date. Subjects not experiencing an event based on their per protocol data are censored at the last EDSS prior to per protocol exclusion without an EDSS increase as for the main analysis.

5.4.2.4.2.2 Time to 24-week CDA up to EOT + 7

The variable for the main analysis described above will be repeated for 24-week CDAs up to EOT + 7. The onset date of the 24-week CDA must be up to EOT + 7 days; the confirmation of the 24-week CDA can be on-treatment or based on post-treatment data. Otherwise exactly the same rules as described in Section 5.4.2.3.1 apply. Subjects that are considered not to have 24-week CDA up to EOT + 7 are censored on the last EDSS assessment without an EDSS increase up to EOT + 7 days, following the same rules as described in the previous section.

5.4.2.4.2.3 Time to potential 24-week CDA

24-week CDA requires confirmation of an EDSS increase by a scheduled EDSS assessment 24 weeks after progression onset. A potential onset at the end of the study may not be confirmed due to end of follow-up within the study. For time to potential 24-week CDA up to EOS all subjects censored in the main analysis with an EDSS increase at the last EDSS assessment in the study are considered as having a potential 24-week CDA, although the confirmation is missing. The onset date of the event for these subjects is the first EDSS increase after the last EDSS assessment without increase. Otherwise the same approach for derivation as described in Section 5.4.2.3.1 is followed.

5.4.2.4.2.4 Time to potential 24-week CDA up to EOS or per protocol exclusion

The time to potential 24-week CDA analysis is repeated for time to 24-week CDA up to EOS or per protocol exclusion.

5.4.2.4.2.5 Time to 24-week CDA up to EOS – alternative censoring

24-week CDA events and corresponding time to event are derived as above for the main analysis [see Section 5.4.2.3.1].

Subjects without 24-week CDA event are censored at their last scheduled EDSS assessment – 24 weeks (168 days).

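### Alternative censoring for 12- and 24-week CDA subtracts 84/168 days although events are confirmed from 70/154 days, which inflates the late Kaplan-Meier incidence

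*SAP*

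**What the plan says.** **Event rule.** SAP 5.4.2.3.1 requires a 12-week CDA to be "confirmed by an EDSS increase at a scheduled visit, at least 70 days*, from the onset date of the potential 12-week CDA". Its footnote explains that "the minimum per-protocol allowed time difference between two EDSS assessments scheduled 12 weeks apart is 70 days". For 24-week CDA, section 5.4.2.4.1 sets the corresponding minimum at 154 days. EOT, premature EOT and follow-up visits count as scheduled visits for confirmation.

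**Alternative censoring.** Sections 5.4.2.3.2.5 and 5.4.2.4.2.5 keep the event derivation of the main analysis and change only the censoring date. For 12-week CDA, "Subjects without 12-week CDA event are censored at their last scheduled EDSS assessment" less 84 days. For 24-week CDA, "Subjects without 24-week CDA event are censored at their last scheduled EDSS assessment" less 168 days. Two reasons are given: (a) to make censoring independent of the EDSS outcome, and (b) for the 12-week variable, that "onset of 12-week CDA events can only occur 12 weeks prior to the last scheduled assessment", with a matching statement for 24 weeks.

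**Main rule, for contrast.** "Censoring date is defined as: Date of last EDSS assessment without an EDSS increase" (section 5.4.2.3.1).

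**Use.** Section 9.7.3.3.5 and its 24-week counterpart repeat the main analyses with this variable. Those comprise a stratified log-rank test, a stratified Cox hazard ratio, and Kaplan-Meier estimates every 12 weeks to Week 108.

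**The concern.** Events and censoring run on different clocks. An increase seen 70 to 83 days before the last scheduled EDSS can be confirmed and enters as an event. A subject with the same visit dates and no increase is censored before that onset date, although observed and normal on it. The same holds at 154 to 167 days for 24-week CDA. Late events are then divided by a risk set from which many observed, event-free subjects have been removed. Whether a subject is still followed at the late onset visit depends on the EDSS result, which is what aim (a) sets out to prevent.

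At stake is the reported incidence and the tail of the Kaplan-Meier curve in the CDA sensitivity analysis aimed expressly at informative censoring.

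**Working it through.** **1. The plan's own figures.** 12 × 7 − 2 × 7 gives the SAP's "84 days – 14 days = 70 days". For 24 weeks, 24 × 7 − 2 × 7 = 154 days. Both reproduce. The mismatch with the censoring offsets is 84 − 70 = 14 days and 168 − 154 = 14 days.

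**2. Why the constants must agree.** Let L be the last scheduled EDSS, g the gap from an earlier visit to L, m the minimum confirmation interval and c the censoring offset. An onset at L − g is confirmable at L if g ≥ m. An event-free subject with the same dates is at risk at L − g only if L − c ≥ L − g, that is g ≥ c. The two conditions agree only when c = m. With m = 70 and c = 84 they disagree for 70 ≤ g < 84; with m = 154 and c = 168, for 154 ≤ g < 168.

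**3. An example inside the visit windows.** Nominal days in SAP Table 9 are 589 (Week 84), 673 (Week 96) and 757 (Week 108). Let the last EDSS fall on Day 750, within ±7 days of Week 108.
- 12-week: onset on Day 673 is confirmed after 750 − 673 = 77 days (≥ 70), so it is an event. The event-free twin is censored at 750 − 84 = Day 666, before Day 673. With 70 days it would be Day 680, still at risk.
- 24-week: onset on Day 589 is confirmed after 161 days (≥ 154). The twin is censored at 750 − 168 = Day 582. With 154 days it would be Day 596.

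This is not rare. If both visit deviations are independent and uniform over the 15 days from −7 to +7, a gap falls below its nominal length with probability (1 − 1/15)/2 = 7/15, about 47%.

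**4. When it disappears.** As far as the extracted Table 3 can be read, an EDSS is scheduled at FU2 but not at FU1. Subjects entering the extension normally end at FU1, so their L is normally Week 108. Subjects not entering have FU2 30-37 days after last dose. With last dose near Day 757, L is Day 787-794, L − 84 is Day 703-710 and L − 168 is Day 619-626. These fall after the Week 96 window (to Day 680) and the Week 84 window (to Day 596). The SAP does not give the share of completers with an FU2 EDSS.

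**5. Size, by simulation.** From the SAP: N = 1133 randomized 1:1, 12-weekly EDSS, confirmation at 70/154 days. Assumed: 10% or 15% control-arm onset by Week 108, hazard ratio 0.8, 15% early withdrawal, visits uniform within ±7 days. Incidence is pooled over arms up to the last confirmable onset, so the reference lies below the assumed onset. Relative excess = (SAP rule ÷ reference) − 1.

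| CDA | Onset | FU2 EDSS | Reference | −84/−168 | Excess | −70/−154 |
|---|---|---|---|---|---|---|
| 12-week | 10% | none | 8.07% | 10.35% | 28% | 8.09% |
| 12-week | 15% | none | 12.16% | 15.68% | 29% | 12.17% |
| 12-week | 15% | 20% | 12.22% | 13.70% | 12% | 12.25% |
| 12-week | 15% | all | 12.23% | 12.36% | 1% | 12.26% |
| 24-week | 10% | none | 7.04% | 9.42% | 34% | 7.04% |
| 24-week | 15% | none | 10.76% | 14.26% | 33% | 10.76% |
| 24-week | 15% | 20% | 10.76% | 12.18% | 13% | 10.76% |
| 24-week | 15% | all | 10.71% | 10.76% | 0.5% | 10.68% |

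With no FU2 EDSS, only 6-7% of events fall after the SAP's censoring point, but they meet very small risk sets. In the 24-week, 15%, no-FU2 case the median risk set at the last event is 68 under the SAP rule and 860 under −154. One event then adds about 1/68 = 1.5 percentage points instead of 1/860 = 0.1. If visit deviations have an SD of 3 days instead, the no-FU2 excess is larger: 16.53% against 12.14% (36%) for 12-week and 15.95% against 10.69% (49%) for 24-week, at 15% onset.

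A separate simulation with 12% onset and 12% dropout agrees: 13.8% against 10.7% (12-week) and 12.4% against 9.5% (24-week) with no FU2 EDSS; 11.6% and 10.4% if 30% of completers have one.

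**6. Treatment comparison.** In these runs the hazard ratio under −84/−168 and under −70/−154 agrees to within 0.001 (for example 0.798 and 0.799). Null rejection at the 5% level is 0.05 under both for 12-week, and 0.06 against 0.07 for 24-week.

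**The case against.** The strongest reply is that little of consequence is damaged. These are supportive variants; alpha is spent on the main analyses, which use another censoring rule. What is repeated is chiefly a log-rank test and a hazard ratio, and step 6 shows both practically unmoved when visit timing is equal across arms. The excess sits in the last confirmable onset window (and in each early withdrawer's last window), so earlier Kaplan-Meier estimates are largely unaffected. Its size turns on the FU2 share, which is unknown. The time-to-potential-CDA analyses address unconfirmed late increases separately. All of this stands and limits the point to incidence and the curve tail. It does not rescue the stated reason, which holds only on the nominal schedule and contradicts the SAP's own 70- and 154-day rules.

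A reader might infer that a difference between this analysis and the main one could not be interpreted. The figures do not support that: the treatment comparison is practically the same under either offset.

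A reader might also infer that the main censoring rule should be replaced. Under 12% onset the main rule gives 10.6-10.7% against a true 10.7% at the last confirmable visit (12-week) and 9.2-9.4% against 9.5% (24-week), which is nearly unbiased for what can be observed.

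Finally, the offset gives non-positive times for very early last visits (Day 80 − 84 = Day −4), and these sections set no floor. Such subjects add almost nothing to any risk set, so this is a matter of tidiness.

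**Conclusion.** The rule is wrong as written for both variables. The rationale is off by 14 days, and censoring still depends on EDSS outcome, contrary to aim (a). The consequence is an upward bias in the Kaplan-Meier incidence around Week 96 (12-week) or Week 84 (24-week). Under assumed 10-15% onset and visits spread within ±7 days, the bias is about 1% relative if all completers have an FU2 EDSS and about 30% if none do, and larger under some other visit-timing assumptions. The direction is certain; the size depends on inputs that the SAP does not give. The claim does not extend to the hazard ratio, the log-rank test or the alpha-controlled main analyses, on the assumption that visit timing is the same in both arms.

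**What to change.** - In 5.4.2.3.2.5, censor event-free subjects at the last scheduled EDSS minus 70 days; in 5.4.2.4.2.5, minus 154 days. Floor both at Day 1.
- Correct the rationale in both sections to say that a confirmable onset can occur no later than 70 (or 154) days before the last scheduled EDSS.
- Leave the main censoring rule in 5.4.2.3.1 and 5.4.2.4.1 as it is.

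The cost is two constants, a floor and a few words. No events are lost and no new data are needed.

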5.4.2.4 Time to 24-week CDA

5.4.2.4.1 Main analysis of secondary endpoint

The derivation of the variables for Time to 24-week CDA up to EOS follows the same approach as described in Section 5.4.2.3.1, but onset of progression is to be confirmed after 24 weeks (≥ 154 days, i.e., 168 days – two times 7-day visit time window) instead of after 12 weeks. The progression has to be persistent between onset and confirmation.

5.4.2.4.2 Variables for supplementary analyses

5.4.2.4.2.1 Time to 24-week CDA up to EOS or per protocol exclusion

Time to 24-week CDA for the per protocol analysis is derived in the same way as for the variable for the main analysis, but only based on EDSS assessments conducted prior to first occurrence of a deviation leading to exclusion from per protocol [see Section 7.1.3].

Also, deaths due to MS are only considered up to that date. Subjects not experiencing an event based on their per protocol data are censored at the last EDSS prior to per protocol exclusion without an EDSS increase as for the main analysis.

5.4.2.4.2.2 Time to 24-week CDA up to EOT + 7

The variable for the main analysis described above will be repeated for 24-week CDAs up to EOT + 7. The onset date of the 24-week CDA must be up to EOT + 7 days; the confirmation of the 24-week CDA can be on-treatment or based on post-treatment data. Otherwise exactly the same rules as described in Section 5.4.2.3.1 apply. Subjects that are considered not to have 24-week CDA up to EOT + 7 are censored on the last EDSS assessment without an EDSS increase up to EOT + 7 days, following the same rules as described in the previous section.

5.4.2.4.2.3 Time to potential 24-week CDA

24-week CDA requires confirmation of an EDSS increase by a scheduled EDSS assessment 24 weeks after progression onset. A potential onset at the end of the study may not be confirmed due to end of follow-up within the study. For time to potential 24-week CDA up to EOS all subjects censored in the main analysis with an EDSS increase at the last EDSS assessment in the study are considered as having a potential 24-week CDA, although the confirmation is missing. The onset date of the event for these subjects is the first EDSS increase after the last EDSS assessment without increase. Otherwise the same approach for derivation as described in Section 5.4.2.3.1 is followed.

5.4.2.4.2.4 Time to potential 24-week CDA up to EOS or per protocol exclusion

The time to potential 24-week CDA analysis is repeated for time to 24-week CDA up to EOS or per protocol exclusion.

5.4.2.4.2.5 Time to 24-week CDA up to EOS – alternative censoring

24-week CDA events and corresponding time to event are derived as above for the main analysis [see Section 5.4.2.3.1].

Subjects without 24-week CDA event are censored at their last scheduled EDSS assessment – 24 weeks (168 days).

This alternative censoring algorithm is applied (a) to ensure independence of censoring from the EDSS outcome and consequently avoid informative censoring and (b) to reflect that onset of 24-week CDA events can only occur 24 weeks prior to the last scheduled assessment.

5.4.3 Exploratory MRI efficacy variables

MRI data are provided from a central reader.

Baseline

The central reader defines the result from ‘Visit 2 - Baseline’ as baseline (or ‘Visit 2a - Baseline 2nd attempt’ if available) and uses that Baseline visit as a reference in derivations of various variables (e.g. new or enlarging T2 lesions).

For analysis, baseline for MRI variables is defined in the same way, i.e., Visit 2 unless Visit 2a is available. In the unexpected case a Visit 2 scan is conducted after randomization, it is still considered as baseline.

MRI at [REDACTED] or at [REDACTED] visit windowing

MRI variables at [REDACTED] or [REDACTED] are based on the result from the corresponding nominal visit (or from a re-mapped premature EOT visit [see Section 11.3]). In case of missing results, MRI results from an unscheduled visit can be re-mapped to a scheduled visit if conducted during the time window specified in Section 11.3. Care needs to be taken however in derivation of cumulative variables where occasionally unscheduled MRIs are not included, as per the respective derivation details.

Handling of missing MRI results at [REDACTED] at [REDACTED]

If MRI at [REDACTED] or [REDACTED] is missing, a last observation carried forward (LOCF) approach is implemented. The last MRI scan up to the visit window upper limit as specified in Section 11.3 is considered. Baseline information is not carried forward.

5.4.3.1 Number of [REDACTED] at [REDACTED] and [REDACTED]

The [REDACTED] per visit is derived as the sum of [REDACTED] at that visit.

Handling of missing MRI results at [REDACTED] or [REDACTED] follows the general rules for MRI data described in Section 5.4.3 above. [REDACTED] LOCF and [REDACTED] LOCF variables are also derived.

The [REDACTED] to [REDACTED] is derived as the sum of [REDACTED]. This includes [REDACTED] scans if available. It may include [REDACTED] if it is the [REDACTED], following selection of [REDACTED]. To account for a potentially varying number of scans contributing to the variable, the analysis will be adjusted by the ‘Number of MRI scans’ included in the derivation. Similarly, the [REDACTED] to [REDACTED] is derived.

The [REDACTED] All other derivations follow the same approach as

above for lesions up to [REDACTED]. To account for a potentially varying number of scans contributing to the variable, the analysis will be adjusted by the 'Number of [REDACTED] is derived.

Note: The number of [REDACTED] At baseline [REDACTED] are not available, thus no corresponding record is expected.

Note: [REDACTED] are assumed to not enhance for more than 12 weeks. This requires handling of data as follows:

- *If at a visit, number of [REDACTED] are not recorded, the number of [REDACTED] Rationale: As per [REDACTED] t and [REDACTED]*
- *If at a [REDACTED] is recorded, these [REDACTED] are considered implausible and therefore not to be considered in derivations of [REDACTED].*

